16.3 Volunteer Information and Informed Consent

Informed consent should be obtained by means of a VIS and ICF, prepared in accordance with ICH E6 Section 4.8.10 and applicable local regulations, written in non-technical language. All volunteers will be provided with oral and written information describing the nature and duration of the study and the procedures to be performed. The volunteer will be asked to sign and date an ICF prior to any study-specific procedures being performed. No volunteer can enter the study before his/her informed consent has been obtained. A sample volunteer ICF used in the study will be included in the clinical study report for this protocol.

Prior to study start, the volunteers will receive a full explanation of the nature of the study, its purpose, the procedures involved, the expected duration, the potential risks and benefits involved, and any potential discomfort. Each volunteer must be informed that participation in the study is voluntary and that he/she may withdraw from the study at any time and that withdrawal of consent will not affect his/her subsequent medical treatment or relationship with the treating physician. The volunteer should understand the VIS and ICF before signing and dating the ICF. The Investigator or person obtaining consent must also sign and date the form. Each volunteer will be given a copy of the signed informed consent and written information.

The original signed ICF for each volunteer will be verified by the Sponsor monitors and kept in the study centre investigational site files.

17. GENERAL OBLIGATIONS, AGREEMENTS AND ORGANISATION

17.1 Data Protection and Confidentiality

Data protection will be carried out in accordance with the Principles of the Data Protection Act (1998) 95/46/EC. This will apply to all study data in whatever format it is collected and recorded.

17.2 CRFs and Handling

Electronic CRFs will be used in this trial. Should any corrections or amendments be necessary, data clarification requests will be forwarded to the Investigator or designee.

17.3 Quality Control and Monitoring

The conduct of the study will be monitored by appropriately qualified staff from the Sponsor and/or an organisation authorised to conduct activities on the Sponsor's behalf. The Sponsor will retain the responsibility for monitoring and may delegate this responsibility via a contract and/or Monitoring Manual.

The study will be monitored at regular intervals and the frequency of monitoring visits will be determined by the rate of volunteer recruitment. The following will be reviewed at these visits:

- Responsibilities of the Investigator and the study site under GCP requirements
- Compliance with the protocol
- Consent procedure
- Source Data Verification (SDV)
- Procedures for AEs
- Storage and accountability of study vaccine

The purpose of SDV is to verify, so far as is possible, that the information in the CRF reflects the data recorded in the volunteer's source data records. SDV will be performed with due regard for volunteer confidentiality. SDV will be undertaken on an ongoing basis as part of the monitoring visits. Direct access to the source documents will be required. The monitor will make a direct comparison with data entered in the volunteer CRFs and the source data.

The Investigator must permit the monitor, the Sponsor's internal auditors and representatives from the Regulatory Authorities to inspect all study-related documents and pertinent source data records for confirmation of data contained within the CRFs.

17.4 Quality Assurance, Audit and Inspection

This study may be subject to audit by the CRO, Sponsor or their representatives and Regulatory Authorities. These audits may be undertaken to check compliance with the requirements of GCP and can include:

- In-house study file audit
- Audit of computer database

- Audit of Clinical Study Report
- Audit of selected study sites, requiring access to volunteer medical records, study documentation and facilities, laboratories or pharmacies used for the study.

The study site, facilities and all data (including source data) and documentation will be made available for audit by the Investigator according to the ICH-GCP guidelines. The Investigator agrees to co-operate with the auditor during his/her visit and will be available to supply the auditor with CRFs or other files necessary to conduct that audit. Any findings will be strictly confidential.

In the event that a Regulatory Authority informs the Investigator that it intends to conduct an inspection, the Sponsor must be notified immediately.

17.5 Storage of Study Documents

The circumstances of completion or termination of the study notwithstanding, the Investigator has the responsibility to retain all study documents, including but not limited to the protocol, copies of CRFs, Investigator's Brochure, regulatory agency registration documents, ICFs, and EC correspondence.

The site will retain study documents for 15 years after completion of the study. This will include copies of the CRF. At the end of the 15 year period the site will contact the Sponsor who will determine any future arrangements for the storage of the study documents.

All CRFs and clinical trial data will be stored by the Sponsor or designee for a period of at least 15 years after termination of the study. The volunteer consent forms and re-identification lists will be archived with the Investigator for at least 15 years after termination of the study.

17.6 Registration and Publication of Study and Results

The trial will be registered by the Sponsor on a publicly accessible database e.g. <http://www.controlled-trials.com>.

The trial results will not be published without written consent by the Sponsor. Any oral or written communications /publications concerning the trial results will be reviewed and approved in writing by the Sponsor, which has a 60-day period to respond after receipt of the proposed communication/publication.

18. SCHEDULE OF ASSESSMENTS

Part A Schedule of Assessments

	Screening Period	Treatment Period								Post-Study Medical	Safety Follow-Up
	Visit 1	Visit 2	Visit 3	Visit 4	Visit 5	Visit 6	Visit 7	Visit 8	Visit 9	Visit 10	Visit 11
Assessment	Day -28 to Day -1	Day 1	Day 2	Day 8	Day 15 ^a	Day 29 ^b	Day 30 ^{b,c}	Day 43 ^b	Day 57 ^b	Day 85	Day 183 ^a
Informed Consent	X										
Inclusion/ Exclusion Criteria	X										
Demography	X										
Medical History	X										
Physical Examination ^d	X	X								X	
Height, Weight, BMI	X										
Vital signs ^e	X	X ^f	X	X		X ^{g,h}	X	X		X	
12-lead ECG	X									X	
Urinalysis	X			X				X		X	
Safety laboratory tests	X			X				X		X	
HIV, Hep B and Hep C	X										
Pregnancy test ⁱ	X	X				X ^h				X	
Alcohol breath test	X	X									
Urine drugs of abuse test	X	X									
Review of volunteer eligibility		X									
Randomisation		X									
Administration of primary dose ^l		X									
Administration of booster dose						X ^h					
PD blood sample – antibody response		X				X		X	X	X	
Brief medical examination ^k		X				X					
Assessment of injection site(s) ^l			X	X		X ^m	X	X	X	X	
AE check						X				X	X
Con med check	X					X				X	

Footnotes

- a. Visit performed by telephone.
- b. Day numbers of Visits 6, 7, 8 and 9 may change if the dosing regimen is changed.
- c. Visit 7 not required if booster dose not administered.
- d. Full physical examination at screening and post-study medical. Brief physical examination prior to first dose.
- e. Heart rate, blood pressure, tympanic temperature and respiration rate.
- f. Vital signs at Visit 2 will be recorded pre-dose and at 2 and 6 hours post-dose.
- g. Vital signs at Visit 6 will be recorded pre-dose and at 2 hours post-dose.
- h. Administration of booster dose only if applicable to this cohort. If booster dose not administered, vital signs and pregnancy test are not to be performed.
- i. Serum pregnancy test at screening and post-study medical. Urine pregnancy test prior to each dose.
- j. Sentinel dosing for all cohorts for the primary dose only.
- k. Brief medical examination (including assessment of the injection site(s) to determine eligibility for discharge at least 8 hours post-dose on Day 1 and at least 4 hours post-dose on Day 29.
- l. Photographs may be taken of injection site reactions as required.
- m. Assessment of first injection site, to be assessed pre-dose.

Part A Schedule of Assessments – Exploratory Assessments

	Treatment Period				Post-Study Medical
	Visit 2	Visit 6	Visit 8	Visit 9	Visit 10
Assessment	Day 1	Day 29	Day 43	Day 57	Day 85
Ig ELISA	C1-C6	C1-C6	C1-C6	C1-C6	C1-C6
[REDACTED]	[REDACTED]	[REDACTED]	[REDACTED]	[REDACTED]	[REDACTED]
[REDACTED]	[REDACTED]	[REDACTED]			[REDACTED]
[REDACTED]	[REDACTED]				[REDACTED]
[REDACTED]	[REDACTED]				[REDACTED]
[REDACTED]	[REDACTED]	[REDACTED]	[REDACTED]	[REDACTED]	[REDACTED]

(C = cohort)

Part B Schedule of Assessments

	Screening Period	Treatment Period																		Post-Study Medical	
	Visit 1	Visit 2	Visit 3	Visit 4 ^a	Visit 5	Visit 6	Visit 7 ^b	Visit 8	Visit 9	Visit 10	Visit 11	Visit 12 ^a	Visit 13	Visit 14 ^a	Visit 15	Visit 16 ^a	Visit 17	Visit 18 ^a	Visit 19 ^a	Visit 20	
	Day -28 to Day -1	Day 1	Day 2	Day 8	Day 15	Day 29	Day 30	Day 43	Day 57	Day 85	Day 113	Day 141	Day 169	Day 197	Day 225	Day 253	Day 281	Day 309	Day 337	Day 365	
Assessment				Week 1	Week 2	Week 4		Week 6	Week 8	Week 12	Week 16	Week 20	Week 24	Week 28	Week 32	Week 36	Week 40	Week 44	Week 48	Week 52	
Informed Consent	X																				
Inclusion/Exclusion Criteria	X																				
Demography	X																				
Medical History	X																				
Physical Examination ^c	X	X																			X
Height, Weight, BMI	X																				
Vital signs ^d	X	X ^e	X		X	X ^{f,g}	X	X	X	X	X		X		X		X				X
12-lead ECG	X																				X
Urinalysis	X				X			X													X
Safety laboratory tests	X				X			X													X
HIV, Hep B and Hep C	X																				
Pregnancy test ^h	X	X				X ^g				X											X
Alcohol breath test	X	X																			
Urine drugs of abuse test	X	X																			
Review of volunteer eligibility		X																			
Randomisation		X																			
Administration of primary dose		X																			
Administration of booster dose						X ^g															
Streptococcus B swab – vaginal		X				X			X	X	X		X		X		X				X
Streptococcus B swab – rectal		X				X			X	X	X		X		X		X				X
PD blood sample – antibody response		X			X	X		X	X	X	X		X		X		X				X
Brief medical examination ⁱ		X				X															
Assessment of injection site(s) ^j			X		X	X ^k	X	X	X	X	X		X		X		X				X
AE check												X									X
Con med check	X											X									X

Footnotes

- Visits 4, 12, 14, 16, 18 and 19 conducted by telephone.
- Visit 7 not required if booster dose not administered.
- Full physical examination at screening and post-study medical. Brief physical examination prior to first dose.

- d. Heart rate, blood pressure, tympanic temperature and respiration rate.
- e. Vital signs at Visit 2 will be recorded pre-dose and at 2 hours post-dose.
- f. Vital signs at Visit 6 will be recorded pre-dose and at 2 hours post-dose.
- g. Administration of booster dose only if applicable to this cohort, If booster dose not administered, vital signs, and pregnancy test are not to be performed.
- h. Serum pregnancy test at screening and post-study medical. Urine pregnancy test prior to each dose and at Visit 10.
- i. Brief medical examination (including assessment of the injection site(s)) to determine eligibility for discharge at least 2hours post-dose on Day 1 and at least 2 hours post-dose on Day 29.
- j. Photographs may be taken of injection site reactions as required.
- k. Assessment of first injection site, to be assessed pre-dose.

Part B Schedule of Assessments – Exploratory Assessments

	Treatment Period								Post-Study Medical
	Visit 2	Visit 5	Visit 6	Visit 8	Visit 9	Visit 10	Visit 11	Visit 13	Visit 20
	Day 1	Day 15	Day 29	Day 43	Day 57	Day 85	Day 113	Day 169	Day 365
Assessment		Week 2	Week 4	Week 6	Week 8	Week 12	Week 16	Week 24	Week 52
Ig ELISA	C1 or C2	C1 or C2	C1 or C2		C1 or C2	C1 or C2		C1 or C2	C1 or C2
[REDACTED]	[REDACTED]		[REDACTED]		[REDACTED]	[REDACTED]		[REDACTED]	[REDACTED]
[REDACTED]			[REDACTED]		[REDACTED]	[REDACTED]			[REDACTED]
[REDACTED]					[REDACTED]	[REDACTED]			[REDACTED]
[REDACTED]					[REDACTED]	[REDACTED]			[REDACTED]
[REDACTED]	[REDACTED]	[REDACTED]		[REDACTED]		[REDACTED]	[REDACTED]		[REDACTED]

(C = cohort)

Note: Cohort 1 or 2 to be selected based on results from Part A. Timepoints for sample collection may be altered based on results from Part A.

a) Time point not entirely fixed and dependent on results obtained in Part A.

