7. STUDY OBJECTIVES AND ENDPOINTS

7.1 Primary Objective

The primary objective is to evaluate the safety and tolerability of the GBS-NN vaccine for 12 weeks after the first dose of vaccine.

The following endpoints will be evaluated to support this objective: local and systemic reactogenicity; adverse events; laboratory tests; urinalysis; vital signs; 12-Lead ECG parameters; physical examination.

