Visit 4 will be performed 1 week after administration of the primary dose. An assessment of the injection site will be performed, vital signs will be recorded, safety blood samples for haematology and biochemistry will be collected, urinalysis will be performed and AEs and concomitant medications will be reviewed.

Visit 5

Visit 5 will be performed 2 weeks after administration of the primary dose. This visit will be performed via telephone and a review of AEs and concomitant medications will be performed.

Visit 6

Visit 6 will be performed 4 weeks after Visit 2. A booster dose will or will not be administered at this visit depending on the decision made by the Safety Review Committee for each cohort.

If a booster dose is administered at this visit, the following assessments will be performed: an assessment of the injection site and a pharmacodynamic blood sample will be taken to measure antibody response prior to dosing. A urine pregnancy test will be performed prior to dosing. A booster dose will be administered. Volunteers will remain in the study unit for at least 4 hours post-dose. Vital signs will be recorded pre-dose and at 2 hours post-dose. A brief medical examination (including an assessment of the injection sites) will be performed prior to discharge to ensure the volunteer is fit for discharge.

If a booster dose is not administered at this visit, the following assessments will be performed: an assessment of the injection site and a pharmacodynamic blood sample will be taken to measure antibody response.

AEs and concomitant medications will be reviewed whether a booster dose is administered or not.

Visit 7 (Only if a booster dose is administered)

Visit 7 will be performed 24 hours (\pm 2 hours) after administration of the booster dose and an assessment of the injection sites will be performed, vital signs will be recorded and AEs and concomitant medications will be reviewed. If a booster dose is not administered, this visit will not be performed.

Visit 8

Visit 8 will be performed 2 weeks following Visit 6 and the following assessments will be performed: an assessment of the injection sites, vital signs will be recorded, safety blood samples for haematology and biochemistry will be collected, urinalysis will be performed, a pharmacodynamic blood sample will be taken to measure antibody response and AEs and concomitant medications will be reviewed.

Visit 9

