12.3 Safety Assessments

The description of safety assessments is given below, and the timings of these assessments is given in the Schedule of Assessments. The time points of the safety assessments may change depending on information gained throughout the study, however the total number of safety assessments per volunteer will not be reduced, although unscheduled assessments may be performed at the discretion of the Investigator.

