12.6 Individual Volunteer Stopping Criteria

Volunteers who meet one or more of the following stopping criteria will receive no further doses of study vaccine but will be followed up for safety:

- Severe injection site reaction, see Appendix 1
- Severe systemic reaction, e.g. anaphylaxis, see section 14.2.1
- Persistent febrile reaction (>38.9°C and >24 hours) at the Investigator's discretion
- SAE related to the study agent

The medical safety of the volunteer is of paramount importance when discussing study continuation.

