Parameter values, position according to laboratory ranges (if available) and investigator assessment will be described according to visit for each treatment/dose group. In order to study evolution of parameters after vaccination, parameter values changes from pre- to post-dose visits will be performed. Emergent values (for parameters with available laboratory ranges) with their corresponding position according to ranges will be listed by treatment/dose group and volunteer.

- **Urinalysis**

Urinalysis will be performed at V1 (screening), V4 (part A), V5 (part B), V8 (parts A and B) and post-study medical visit (V10 for part A and V20 for part B).

Parameter values (quantitative or binary results, *i.e.* positive/negative), position according to laboratory ranges (if available) and investigator assessment will be described according to visit for each treatment/dose group. In order to study evolution of continuous parameters after vaccination, parameter values changes from screening to post-study medical visit will be performed. Emergent values (for parameters with available laboratory ranges or with binary results) will be listed by treatment/dose group and volunteer.

- **Vital signs**

Vital signs will be characterised by heart rate, blood pressure, tympanic temperature and respiratory rate. Vital signs will be assessed at V1 (screening), V2 (pre-dose, T2h and T3h post-dose), V3, V4 (part A only), V6 (pre-dose and T2h post-dose for volunteers receiving booster dose), V7 (only if administered booster dose), V8, and post-study medical visit (V10 for part A and V20 for part B). For study part B, additional vital signs assessments will be performed at V5, V8, V9, V10, V11, V13, V15 and V17.

Parameter values, position according to reference ranges (if available) and investigator assessment will be described according to visit and assessment time for each treatment/dose group. In order to study evolution of parameters after vaccination, parameter values changes from pre-dose to post-dose assessments will be performed. Emergent values (for parameters with available reference ranges) with their corresponding position according to reference ranges will be listed by treatment/dose group and volunteer.

- **12-lead ECG parameters**

ECG will be assessed at V1 (screening) and post-study medical visit (V10 for part A and V20 for part B).

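### Vital signs are omitted at Visit 6 for anyone not given the booster, so women held back after a reaction, and any one-dose cohort, lack a Day 29 reading of a primary safety endpoint.

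*Combined protocol and SAP*

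**What the plan says.** Section 7.1 sets the primary objective, to "evaluate the safety and tolerability of the GBS-NN vaccine for 12 weeks after the first dose of vaccine", and names vital signs among its endpoints. Section 15.4.2 summarises them by visit and assessment time for each treatment/dose group and lists emergent values.

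The booster falls at Visit 6 (Day 29). When it is not given, five places agree that no vital signs are taken there:

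- Part A schedule, footnote h: "If booster dose not administered, vital signs and pregnancy test are not to be performed".
- Part B schedule, footnote g: "If booster dose not administered, vital signs, and pregnancy test are not to be performed".
- Section 12.2.1, Visit 6: "If a booster dose is not administered at this visit, the following assessments will be performed: an assessment of the injection site", followed only by the antibody sample. The list in 12.2.2 adds swabs but no vital signs.
- Section 15.4.2 limits the Visit 6 readings to "V6 (pre-dose and T2h post-dose for volunteers receiving booster dose".

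Visit 7, the 24-hour post-booster check, is not held without a booster. Visit 6 is held either way, with review of adverse events and concomitant medication.

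Under 12.6, women with a severe local or systemic reaction, persistent fever or a related SAE "will receive no further doses of study vaccine but will be followed up for safety". No separate follow-up schedule is given for them. Section 12.5 says instead that women who meet those criteria leave the study.

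**The concern.** Under this rule, whether the Day 29 reading exists can depend on how the woman reacted to the first dose. A woman held back for persistent fever could attend Visit 6 and have no temperature scheduled. The Visit 6 pre-dose summary for her dose group would then cover only those who tolerated the first dose well enough to be boosted.

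A one-dose regimen, which 10.1 leaves possible for Part B, would have no Day 29 vital signs to set beside the two-dose regimens.

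An ad hoc reading would not repair the data. Section 12.3 lets the Investigator order unscheduled assessments, but 15.1.1 uses only scheduled values after vaccination. Section 15.1.3 plans tests between groups on primary endpoints, so the readings available to each group matter.

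**Working it through.** The documents state no total number of vital-sign readings, so there is no figure to reproduce. The check is a count from the two schedules and the visit text in 12.2.1 and 12.2.2. It runs from after the first dose to Day 85, the window of the primary objective.

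**Part A, with booster.** Visit 2 gives two post-dose sets ("Vital signs at Visit 2 will be recorded pre-dose and at 2 and 6 hours post-dose"). Visits 3, 4, 8 and 10 give one each, Visit 6 gives two and Visit 7 gives one.
2 + 4 + 2 + 1 = 9.

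**Part B, with booster.** Visit 2 gives one post-dose set (2 hours). Visits 3, 5, 8, 9 and 10 give one each, Visit 6 gives two and Visit 7 gives one.
1 + 5 + 2 + 1 = 9.

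**Without booster, either part.** Visit 6 pre-dose, Visit 6 at 2 hours and Visit 7 are lost.
9 − 3 = 6, and 3/9 = 33%.

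**Separating the three lost sets.**
- Visit 6 at 2 hours and Visit 7 at 24 hours monitor the booster. With no injection there is nothing for them to monitor.
- The Visit 6 pre-dose set is a Day 29 observation that does not depend on an injection. The avoidable loss is therefore 1/9 = 11%.

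**After the fix.** A woman without a booster has 6 + 1 = 7 sets. A boosted woman has 9, of which 9 − 2 = 7 fall at time points common to both.

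**Sensitivity of the count.** Adding the Day 1 pre-dose set gives 10 against 7, so the avoidable loss is 1/10 = 10%. Adding screening gives 11 against 8, or 1/11 = 9%. Section 15.4.2 gives the Visit 2 post-dose times as 2 and 3 hours, which does not match either schedule. If both times applied to Part B, its post-dose count would be 10 against 7.

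**Gap between scheduled readings without a booster.**
- Part A: Day 8 to Day 43, 35 days. With a Day 29 reading this becomes 21 and 14 days.
- Part B: Day 15 to Day 43, 28 days. With a Day 29 reading this becomes 14 and 14 days.

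**Cohort or individual.** The first sentence of each footnote speaks of the cohort, so it could be read as covering only one-dose cohorts. The second sentence is unrestricted, and 15.4.2 is worded by volunteer. The individual reading is therefore the natural one for the analysis, though the footnotes could be clearer.

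**The case against.** The strongest reply is that most of the missing readings should be missing, and that follow-up is otherwise intact. Without a booster, Visit 6 keeps the injection-site check and the adverse event review. Visit 8 keeps vital signs, laboratory tests and urinalysis, and 14.3 requires continuing events to be reviewed at each assessment. That is real safety follow-up, so the footnotes do not defeat 12.6. Nor is a 35-day gap exceptional: every Part A volunteer has no scheduled vital signs from Day 43 to Day 85 (42 days). Section 6.3 expects any febrile reaction to be transient, so a Day 29 reading may well be normal. All of this stands, and it keeps the point small.

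A reader might infer more than the documents support:

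- **That these women lose a third of their safety readings.** The count of 9 against 6 is right, but two of the three sets belong to a dose not given.
- **That the footnotes breach 12.3**, which says "however the total number of safety assessments per volunteer will not be reduced". That clause qualifies later changes to time points. It does not forbid a conditional schedule fixed in advance.
- **That many women could be held back before any review, because 12.7 acts only above 20% of a cohort.** For Part A cohorts 1 to 5, section 12.5 schedules a safety review after Day 8, and 6.2 puts the booster decision at the escalation review. One sentinel reaction or one related SAE also triggers a meeting.
- **That fewer readings would make a one-dose arm look cleaner by a calculable margin.** That needs an out-of-range rate that the documents do not give, and independence between readings in the same woman, which is implausible. It also concerns the chance of at least one emergent value, whereas 15.4.2 plans only to list emergent values.

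The one-dose case is hypothetical: Part A cohorts 1 to 6 are all anticipated as two-dose. Placebo women following the same one-dose regimen would have the same reduced schedule, so only comparisons across cohorts or with pooled placebo would be uneven.

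**Conclusion.** The point holds as a minor one. One set of a primary safety measure, at a visit that is held anyway, is missing by rule for women held back after a reaction and for any one-dose cohort. It is one of nine post-dose sets to Day 85 (11%) in either part. The Visit 6 pre-dose summary excludes reactors, and unscheduled readings cannot enter the statistics. Summaries at other time points are not biased. The documents do not show in which direction, or by how much, the Visit 6 summary would shift, and they do not forecast how many women would be affected.

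This rests on two assumptions: that the no-booster rule applies to individual women as 15.4.2 words it, and that women held back stay in follow-up as 12.6 says. If 12.5 governs and they leave the study, section 9.5 calls for a post-study medical, which includes vital signs. They would still have no Day 29 reading on the schedule.

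**What to change.** 1. Delete vital signs from Part A footnote h and Part B footnote g, leaving the pregnancy-test wording as it is.
2. Add one vital-sign set to the no-booster Visit 6 lists in 12.2.1 and 12.2.2.
3. Change 15.4.2 so that Visit 6 has a pre-dose or single reading for all volunteers, with the 2-hour reading for boosted volunteers only.
4. Summarise the Visit 6 pre-dose or single reading on all ITT volunteers who attend.
5. Base any between-group comparison of emergent vital-sign values on time points common to all groups. Show Visit 6 at 2 hours and Visit 7 separately for boosted volunteers.
6. Reconcile 12.5 with 12.6 on whether women who meet an individual stopping criterion leave the study or remain in follow-up, and state which visits they attend.

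The cost is protocol wording and one reading after five minutes' rest (12.3.2) at an existing visit. No visit or blood sample is added.
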